8.1.2 Altered Enrollment Ratio for Apo E Variants

Triglyceride handling varies by apolipoprotein E (apoE) status. There are 3 common alleles for apoE: ApoE2, ApoE3, and ApoE4. The normal allele is ApoE3, so most individuals have ApoE3/E3. However, the other alleles are sufficiently common that we will likely have alternative genotypes in the study. Certain functional variations in the ApoE gene appear to cause effect modification on 1. fish oil kinetics and 2. postprandial triglyceridemia. Thus, it is especially important that people with phenotypes influenced by ApoE variants do not inadvertently cluster into one group or the other. Since alternative phenotypes are common enough to be expected, but still remain in the minority, stratification by a 2:1 ratio would be problematic because we may or may not get a match for a patient with a given phenotype. Therefore, if we enroll a person with an ApoE2 phenotype (genotypes 2/2 or 2/3) or ApoE4 phenotype (genotypes 3/4 or 4/4), we will attempt to balance them 1:1 between usual care and active EPA-rich oil. This is an exception to the targeted 2:1 ratio for most subjects, who will have the Apo E3 phenotype (genotypes 3/3 or 2/4). We will revisit the issue of ApoE variants during the interim analysis, which may motivate the alternative approach of designing a substudy to allow crossover for people with ApoE variants. Doing so would assure balance, but also improve power through statistical efficiencies of the crossover design for this rarer population. If the pilot data support a crossover approach for the variants, we would do so as a substantial protocol amendment. At this stage, we will simply gather data under the parallel design to inform that decision.

	Apo E2 Response		Apo E3 Response		Apo E4 Response	
Genotype	2/2	2/3	3/3	2/4	3/4	4/4
Population Frequency	1%	10%	62%	2%	20%	5%
Fish Oil ¹	↓↓ TG ↓ small dense LDL ↑ HDL		↓ TG ↓ small dense LDL ↑ HDL		↓ TG ↓↓ small dense LDL ↓ HDL ↑↑ LDL	
Low Fat Diet ^{2,3}	↓ LDL ↑ small dense LDL		↓↓ LDL ↔ small dense LDL		↓↓↓ LDL ↓ small dense LDL	
Moderate Fat Diet ³	↔ LDL ↔ small dense LDL		↓ LDL ↓ small dense LDL		↓ LDL ↑↑ small dense LDL	
Moderate Alcohol ⁴	↑ HDL ↓ LDL		↑ HDL		↓ HDL ↑ LDL	
Effective Drug Response	Atorvastatin Pravastatin Lovastatin		No distinction		Probucol Simvastatin	

1. Minihane AM et al. *Arterioscler Thromb Vasc Biol.* 2000 Aug; 20(8):1990-7.
2. Masson LF et al. *Am J Clin Nutr.* 2003;77:1098-111.

8.1.3 Stratification

To limit potential for confounding by triglycerides, we will attempt to balance randomization by TG > 350 mg/dL, so that very triglyceridemic people do not cluster in one group by chance alone. This stratification applies to people without functional Apo E variants (i.e. 3/3 and 2/4), but is not practical for those with functional variants because of their relative scarcity.

8.2 Techniques to Limit Variability

Intensive techniques such as lipoprotein kinetics offer the opportunity to control sources of variability. In this study, we plan to test several methods aimed at reducing measurement variability. For example, we will collect blood at more time points than is often done for kinetic studies, and in particular, we will over-sample the ends. In theory, this could help to mitigate the effect of an outlier at the start or end of the tracer enrichment period, which might otherwise be disproportionately influential. Likewise, we are oversampling regions of the postprandial curve when we anticipate rapid changes to reduce variability around critical points.

8.3 Statistical Methods

We will develop a separate Statistical Analysis Plan (SAP), but describe our general approach here. We will begin the analysis by fully describing data, including aspects of data quality, and will summarize outcomes and explanatory variables, using graphical methods (e.g. Tukey’s notch plots and “spaghetti” plots) in order to evaluate data quality and examine distributional parameters (especially normality). We will evaluate analytes over time to assess patterns of change, and will examine subject-specific values and treatment group summaries over time. Interval variables will be summarized using means and standard deviations as well as medians and interquartile ranges. Categorical variables, including dichotomous factors, will be summarized by proportions. We will characterize the amount and patterns of missing data, if any, and will use transformations if needed to yield variables that conform to the distributional assumptions underlying the analytic techniques. For instance, some continuous variables may be transformed to log scales, as needed to reduce skew, or when multiple continuous variables are in the same model, optimized multivariable Box-Cox transformation.

Our general modeling approach is to use mixed or random effects panel regression (e.g. mixed or gsem in Stata), with treatment assignment and sex as categorical variables and subject as a random intercept (and/or slope), to model each outcome as the dependent variable. Initially we will model period as a categorical variable as well as a period x treatment interaction. On an exploratory basis we will include terms for apoE phenotype and/or baseline triglycerides. In any models with random slopes, we will determine the optimal covariance pattern empirically as that with the lowest Bayesian information criterion (BIC). Hypotheses are two-tailed, and statistical significance for hypothesis testing is initially set at an alpha < 0.05, but expended after interim analysis. If any of the assumptions underlying the analysis methods are violated, we will perform the analyses using alternative statistical methods as appropriate.

Our statistical approach to the adaptive elements accords with the FDA's draft "Guidance for Industry: Adaptive Design Clinical Trials for Drugs and Biologics," v2010. Specifically, the early look at pooled variability will not utilize information about treatment assignment, so as to limit alpha expenditure. On the other hand, the later look will utilize treatment assignment, thus inflating the Type I error rate. Accordingly, we will then re-set the customary alpha from $p < 0.05$ to a "tighter" limit as recommended, per the SAP.

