Statistical Methodology	The focus of the pilot phase is to develop estimates of critical statistical parameters, including central tendency and variability. If the study progresses to the confirmatory phase, in general hypothesis testing will be by mixed effects linear regression with group and time as fixed effects and subject as a random effect with the alpha expended below 0.05 to account for the interim look.

*Although the experimental intervention is already approved for marketing, the pilot nature, small sample size, and mechanistic purpose meet the regulatory definition of Phase I (cf. 21 CFR § 312.21 and discussion below).

1 Introduction

This document is a protocol for a human research study. This study is to be conducted according to US and international standards of Good Clinical Practice (FDA Title 21 part 312 and International Conference on Harmonization guidelines), applicable government regulations and Institutional research policies and procedures.

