2.1 Mechanistic Hypotheses

2.1.1 Hypothesis M1 (Primary Hypothesis, Pilot and Confirmation Stages)

EPA-rich oil retards the VLDL production rate compared with usual care and in the confirmation stage, compared to EPA-poor oil, as determined by apoB-100 before and after therapy by compartmental modeling.

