Subjects will initially be treated with a statin for a minimum of 4 weeks prior to the first kinetic study. Subjects will undergo a lipoprotein kinetic study during Phase 2 and after treatment in Phase 4. Briefly, subjects will drink 4 doses (52mL per dose) of 70% deuterium oxide (aka “heavy water” or D2O) over a one hour period before a bolus injection of [1,1,2,3,3-²H₅]-glycerol (aka D5-glycerol) (100 μmol/kg body weight) and [5,5,5-²H₃]-L-leucine (also known as D3-leucine) (10 μmol/kg body weight). Both the glycerol and leucine boluses will be prepared in 20mL volumes. This is immediately followed by a constant infusion of D3-leucine (10 μmol/kg body weight/hour) (12 μmol/kg body weight/hour for shortened kinetics visit) over a 13-hour (10 hours for shortened kinetics visit) period under constantly-fed conditions: Subjects drink Pediasure (an iso-caloric drink consisting of ~33% fat) every hour for 5 hours and thereafter every other hour (12 servings total). We will collect blood samples before the tracer boluses and 1, 2, 4, 6, 8, 10, 11, 12, 12.5, and 13 hours post-bolus to determine the kinetics of apolipoprotein (apo) B100 in VLDL, very low-density lipoprotein, and low density lipoprotein (LDL). We will also collect 2 kinetics samples the next day, roughly between the hours of 6am to 12pm (indicated on the table as $\pm 03:00$; the corresponding range for minutes post-tracer would be ± 180). Each sample will be separated by 15 to 30 minutes. Subjects will be instructed to drink a Pediasure (13th one) and take their study medication if applicable 1 hour before the first time-point. These Kinetics Day 2 samples are optional and set up this way at it may be difficult for subjects to return to the clinic the next day. The range of time points will not negatively impact the analysis, as long as the correct time of the shake and blood draws are documented. In general, we would strive to get more than one specimen at the end, so that the last part of the regression line doesn’t depend on a solitary data point. Archive samples will also be obtained for possible determination of VLDL Triglyceride (TG) as well as intermediate-density lipoprotein (IDL) apoB and LDL cholesterol kinetics. The kinetics models may be influenced by changes in plasma volume. Since plasma volume changes seasonally, and pre- and post-therapy kinetics may span seasonal transitions, we will estimate plasma volume and its changes throughout the duration of the study and within the prolonged kinetics visit, using BIA to measure various water compartments and Hgb/Hct at various times during the kinetics visit.

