8.1 Sample Size Determination

8.1.1 Sample Size

Since data specific to EPA are not available, the study is formally designed as a pilot study to determine relevant statistical parameters to design a definitive study (e.g. mean, standard deviation, and shape of distribution for outcomes). Since African Americans differ substantially from Caucasians in triglyceride metabolism, at this stage we will limit participation to Caucasians to limit effect modification. This is especially important at the Pilot Stage because effect modification could disproportionately bias the estimates of statistical parameters, and thus, potentially misinform the anticipated Confirmation Stage. If this study affirms expected benefits, it would warrant future study of African Americans, but at this point, doing so might actually undermine the study objectives. One of the adaptive elements of the study design involves the sample size, which may be increased based on interim data under a protocol amendment. The minimum sample size is based on 19 enrollees, 12 assigned to open-label EPA-rich oil and 7 to usual care sans omega-3 oil. Assuming 15% drops from EPA-rich oil and 10% drops from usual care, we anticipate 10 completers assigned to EPA-rich oil and 6 to usual care (Table). The 10 observations on EPA-rich oil should allow us to assess distributional shape.

Screen Fail Rate:	50%	Ratio:	2	1	Attrition Rate:	15%	10%
Screened Population	Enrolled Population			Completer Population			
	Total Subjects	On Drug	No Treatment	Total Subjects	On Drug	No Treatment	
80	40	26	14	34	22	12	
78	39	26	13	33	22	11	
76	38	25	13	32	21	11	
74	37	24	13	31	20	11	
72	36	24	12	30	20	10	
70	35	23	12	29	19	10	
68	34	22	12	28	18	10	
66	33	22	11	27	18	9	
64	32	21	11	26	17	9	
62	31	20	11	26	17	9	
60	30	20	10	26	17	9	
58	29	19	10	25	16	9	
56	28	18	10	24	15	9	
54	27	18	9	23	15	8	
52	26	17	9	22	14	8	
50	25	16	9	21	13	8	
48	24	16	8	20	13	7	
46	23	15	8	19	12	7	
44	22	14	8	18	11	7	
42	21	14	7	17	11	6	
40	20	13	7	17	11	6	
38	19	12	7	16	10	6	
36	18	12	6	15	10	5	
34	17	11	6	14	9	5	
32	16	10	6	13	8	5	
30	15	10	5	12	8	4	

In summary, the essential purpose of the Pilot Stage is to estimate statistical parameters to guide the design of the eventual Confirmation Stage. The sampling plan described above provides a reasonable sample to infer variability and central tendency, especially important to the EPA-rich oil group, for whom there are no data from the lipid kinetics literature.

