Our ability to double-label certain substrates is expected to reduce variability compared to prior studies of fish oil kinetics, as is comparison to usual care sans fish oil rather than a metabolically-active oil. Moreover, the use of an EPA-rich oil may inherently

reduce variability if we are correct that EPA and DHA work at cross purposes somewhat. For these reasons, our empirical standard deviation may be smaller than prior studies. On the other hand, we may have more variability based on heterogeneity of our study population. To mitigate the effect of this uncertainty on power, we will estimate the pooled standard deviation after 6 subjects complete the study to determine the effect size that would be detectable, and may use this information to increase the sample size under a protocol amendment if appropriate. We will begin preliminary tests of the applicable outcomes after 13 subjects are enrolled (that is, both standard deviation *and* effect size), allowing 6 more subjects to accrue while analyzing the interim data. We may use this information to increase the sample size under a protocol amendment (cf Table). We will expend the type I error rate accordingly, so that significance would require a cutoff lower than the customary 0.05 level. This approach will let us adapt the sample size to improve the chances of affirming outcomes that would benefit from additional observations.

Again, the interim analysis would also inform the design of the eventual Confirmation Stage, which again would be submitted as a substantial protocol amendment should it be warranted by the Pilot Stage.

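### The Section 8.3 period-by-treatment term is a valid test of M1, but it uses the Visit 2K baseline inefficiently; name it as the M1 contrast and fit it with a shared baseline mean

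*Combined protocol and SAP*

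**What the plan says.** Section 8.3 describes a mixed or random-effects panel regression "with treatment assignment and sex as categorical variables and subject as a random intercept", and continues: "Initially we will model period as a categorical variable as well as a period x treatment interaction". ApoE phenotype and baseline triglycerides enter on an exploratory basis only. A separate SAP is promised; it is not part of this document.

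The Statistical Methodology row of the Study Summary, which applies only if the study goes beyond the pilot, reads: "in general hypothesis testing will be by mixed effects linear regression with group and time as fixed effects and subject as a random effect". It lists neither sex nor an interaction.

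Hypothesis M1 (Section 2.1.1) concerns the VLDL production rate on EPA-rich oil against usual care, "as determined by apoB-100 before and after therapy by compartmental modeling". The outcome is measured twice: "Subjects will undergo a lipoprotein kinetic study during Phase 2 and after treatment in Phase 4" (Section 7.3.1.1; Visits 2K and 4K). Section 8.1.1 gives the expected size: "we anticipate 10 completers assigned to EPA-rich oil and 6 to usual care".

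On timing, Section 8.1.1 says "We will begin preliminary tests of the applicable outcomes after 13 subjects are enrolled", covering both standard deviation and effect size, and the result may be used to raise the sample size. Section 8.3 confirms that this look is not blind to allocation: "On the other hand, the later look will utilize treatment assignment, thus inflating the Type I error rate".

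**The concern.** In a model with treatment, period and their interaction, the interaction is the between-arm difference in change from Visit 2K to Visit 4K. It is the right quantity for M1. But the treatment main effect lets each arm have its own pre-treatment mean. No treatment has been given at Visit 2K, so apart from the apoE-dependent allocation those means are equal in expectation. Estimating their difference, and then subtracting all of it, adds noise unless the two visits are highly correlated. With about 16 completers that noise is a real share of the error.

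The second issue is that no sentence names the coefficient that tests M1. The Summary's model yields a coefficient on a different scale. That matters most at the allocation-aware look after 13 enrolments, where an effect size is to be estimated and can change the sample size before any confirmatory amendment is written.

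**Working it through.** **Sample sizes.** The plan's figures reproduce by rounding down: 19 x 2/3 gives 12 on drug, leaving 7; 12 x 0.85 = 10.2 gives 10 completers; 7 x 0.90 = 6.3 gives 6. The same rule reproduces all 26 rows of the Section 8.1.1 table. Extended to 13 enrolled (the table stops at 15), it gives 8 v 5 enrolled and, from 6.8 and 4.5, 6 v 4 eventual completers.

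**Formulas.** Set the SD to 1 at both visits, with correlation rho between them (assumed; not in the documents). Let k = sqrt(1/n1 + 1/n0), which is 0.516 at 10 v 6 and 0.645 at 6 v 4.

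- Interaction = on-treatment difference minus baseline difference. Its SE is k x sqrt(2(1 - rho)). A sex main effect does not change this in complete two-visit data.
- Shared-baseline contrast = on-treatment difference minus rho times baseline difference. Its large-sample SE is k x sqrt(1 - rho^2).
- Variance ratio = (1 - rho^2) / (2(1 - rho)) = (1 + rho)/2.

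The large-sample formula flatters the shared-baseline model at this size, because rho must be estimated. The last two columns are therefore simulated (REML random intercept with sex and a two-level apoE term, 12,000 runs).

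| rho | Interaction, 10 v 6 | Shared baseline, large-sample, 10 v 6 | Shared baseline, simulated, 10 v 6 | Interaction, 6 v 4 | Shared baseline, simulated, 6 v 4 |
|---|---|---|---|---|---|
| 0.3 | 0.611 | 0.493 | 0.518 | 0.764 | 0.673 |
| 0.5 | 0.516 | 0.447 | 0.470 | 0.645 | 0.604 |
| 0.7 | 0.400 | 0.369 | 0.383 | 0.500 | 0.485 |
| 0.9 | 0.231 | 0.225 | 0.228 | 0.289 | 0.286 |

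Without sex and apoE the simulated shared-baseline SE at 10 v 6 and rho 0.5 is 0.461, hence the range 0.46 to 0.47.

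**Gain in completers.** To match 16 completers under the shared-baseline model, the interaction needs 16 x (0.611/0.518)^2 = about 22 at rho 0.3, 16 x (0.516/0.470)^2 = about 19 at 0.5 and 16 x (0.400/0.383)^2 = about 17 at 0.7. For scale only, with an assumed 1.0 SD effect at 10 v 6 and sex in the model, power is 44% v 54% at rho 0.5 and 64% v 71% at rho 0.7.

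**The Summary's additive model.** With both visits as outcomes and no interaction, the group coefficient is the average of the baseline and on-treatment differences. Its expectation is (0 + effect)/2, half the effect. Simulation with a true effect of 1.0 SD gave a mean of 0.50; the interaction and the shared-baseline contrast both averaged 1.00.

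**Is a shared baseline justified?** Section 6.1.3 allocates apoE3 subjects 2:1 and apoE2/E4 subjects 1:1. The Section 8.1.2 frequencies give 64% E3 and 36% E2/E4. The expected E2/E4 share is then 0.18/(0.427 + 0.18) = 30% on drug and 0.18/(0.213 + 0.18) = 46% on usual care. Without an apoE term, if variants differ by d SD at both visits, the bias is about 0.16 x d x (1 - rho), or 0.04 SD at d = 0.5 and rho = 0.5. An apoE term removes it for an SE increase of at most 0.02.

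**Unequal variances.** If the treated arm's Visit 4K SD is 1.4 times larger, then at 6 v 4 and rho 0.7 the interaction SE is sqrt((1 + 1.96 - 2 x 0.7 x 1.4)/6 + 0.6/4) = 0.56, against a simulated 0.58 for the shared-baseline model, a small loss. Simulated type I error with Kenward-Roger degrees of freedom and sex in the model was 4.8% to 5.7% with equal variances and 4.8% to 6.0% here.

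**The case against.** The Section 8.3 estimator is valid and in common use, and the pilot makes no power claim. M1 is phrased as a between-arm comparison before and after therapy, and in the Section 8.3 model only the interaction expresses that. A separate SAP is planned, Section 3.1.7 leaves formal testing to an amendment, and Section 1.4 says the Confirmation Stage needs a major protocol revision. All of this stands. It makes the unnamed contrast mostly missing detail.

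The gain rests on an assumed correlation and has gone by rho 0.9. That also stands. The 6 v 4 split is an extrapolation, and tests start after 13 are enrolled rather than completed, so fewer subjects may have Visit 4K data at that look.

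A sharper objection concerns the remedy. Section 8.4 excludes subjects below 80% compliance from the primary efficacy analysis, but only in the active arm. That can unbalance the baselines in a way no apoE term repairs, whereas the unconstrained interaction subtracts a stable baseline difference in full. This is a real limit, and it is why the unconstrained version should be reported alongside.

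Two stronger readings are tempting. One is that the word *initially* signals a rule for dropping the interaction when it is not significant, with an inflated false-positive rate. No section states such a rule, and the next sentence of Section 8.3 goes on to add exploratory terms. The other is that the Summary contradicts Section 8.3. The Summary row covers only the confirmatory phase and is worded as a general approach, so it is better read as abbreviated.

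**Conclusion.** The point holds as an inexpensive improvement to a sound analysis. At 10 v 6 the shared-baseline model lowers the SE by about a tenth at rho 0.5 and about a twentieth at rho 0.7, worth roughly three and one to two completers, with no material gain at rho 0.9. This assumes complete two-visit data, similar variances at the two visits and baseline means that are equal within apoE stratum. The half-effect result for the Summary's group term follows only if that row is taken literally with both visits as outcomes. The documents do not support a claim that the interaction is biased or invalid.

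**What to change.** In Section 8.3, the Summary and the planned SAP, and before the allocation-aware look after 13 enrolments:

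- Name period by treatment on the VLDL-apoB100 production rate as the M1 contrast, retained regardless of its p-value.
- Use the same estimator at the interim and final looks.
- Fit it with a shared baseline mean: the random-intercept model with period, period by treatment and sex, no treatment main effect, and a planned two-level apoE term (E3 v E2/E4). Use REML with Kenward-Roger degrees of freedom.
- Report the unconstrained interaction as a sensitivity analysis, as a check on the one-sided compliance exclusion in Section 8.4.

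The cost is wording, since the Visit 2K value and apoE status are already collected. In return the primary model takes on the shared-baseline and similar-variance assumptions, for a gain that depends on a correlation not yet known.

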5.4.1 When and How to Withdraw Subjects

The PI may withdraw a subject at any time for safety reasons or out of concern for subject adherence to the protocol requirements using clinical and scientific judgment. There are no expected adverse consequences to abrupt cessation of the study medications. Therefore, we don't anticipate any health consequences to major lapses in adherence, withdrawal or subject-initiated discontinuation. As a result, there is no need to titrate off of medications in the event a subject stops participation for any reason. If a subject is withdrawn for safety reasons, we may ask them to return for one or more brief outpatient visits following cessation of study medications to monitor for resolution.

In addition to withdrawing a subject outright, there may be circumstances where a subject may be withdrawn from a particular study procedure without being withdrawn from the entire study. For example, if a subject finds that they cannot tolerate the oral fat challenge, they can be withdrawn from that element of the study but participate in the entire study. Likewise, if a subject develops anemia during the study, the PI may delay or forego visits with heavy phlebotomy, thus averting large-volume phlebotomy. In this case, the subject could remain in the overall study but only have fasting blood draws (i.e. low-volume phlebotomy). Alternatively, since we do not expect the results to be influenced by a secular trend, such visits could be delayed.

This section provides a brief overview of specific stopping rules for individuals who develop 1) a clinically-significant elevation of liver-related clinical laboratory tests and 2) anemia, as detailed below.

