6.1.3 Method for Assigning Subjects to Treatment Groups

The IDS will conduct the randomization for this study, and will assign subjects to the active experimental interventions vs usual care using a computerized randomization technique depending on the apolipoprotein E phenotype (see discussion in Section 7 below). Given that apoE2 and 4 mutations are far less common than apoE3, if we encounter subjects with mutations, we will randomize 1:1 to lessen chances they would cluster on one group or the other.

ApoE Phenotype	Randomization Ratio	Stratification
ApoE3	2:1	TG < 350 vs TG ≥ 350 mg/dL
ApoE2 or ApoE4	1:1	none

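### The allocation ratio depends on apoE phenotype, but the main model leaves apoE to exploratory analysis; the allocation stratum should be pre-specified, as stratum x period

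*Combined protocol and SAP*

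**What the plan says.** Section 6.1.3 assigns ApoE3 subjects 2:1 and treats the other phenotypes differently: "if we encounter subjects with mutations, we will randomize 1:1 to lessen chances they would cluster on one group or the other". Section 8.1.2 gives the same rule ("This is an exception to the targeted 2:1 ratio for most subjects") and defines the groups: ApoE3 is genotype 3/3 or 2/4, and the variants are 2/2, 2/3, 3/4 and 4/4. Its reason is that "Certain functional variations in the ApoE gene appear to cause effect modification on 1. fish oil kinetics and 2. postprandial triglyceridemia".

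The model in 8.3 has treatment, sex, a subject random effect, period and period x treatment. ApoE appears only in this sentence: "On an exploratory basis we will include terms for apoE phenotype and/or baseline triglycerides". The Study Summary, writing in general terms about a possible confirmatory phase, lists fewer terms: "hypothesis testing will be by mixed effects linear regression with group and time as fixed effects and subject as a random effect". Nothing in the document makes the allocation stratum a required term. Section 8.3 describes a general approach ahead of a separate SAP, and 8.1.2 says apoE variants will be revisited at the interim analysis.

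**The concern.** When the probability of receiving treatment depends on a baseline factor, the arms differ in that factor by design, and the analysis should normally condition on it. Here the 1:1 rule, meant to stop variants clustering in one arm, makes them a larger expected proportion of usual care than of the oil arm. A uniform 2:1 ratio would have given equal expected proportions.

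At stake is the treatment contrast. If variants change differently over the study even without oil, the unadjusted contrast is biased, and more subjects do not remove the bias. If apoE only alters the response to oil, the unadjusted contrast is a weighted average of stratum effects with weights that do not match the population. The looks are affected differently. For the standard deviation look after 6 completers, 8.3 says that "the early look at pooled variability will not utilize information about treatment assignment", so it is untouched. The later look uses treatment assignment and effect size ("We will begin preliminary tests of the applicable outcomes after 13 subjects are enrolled") and informs futility, sample size and the EPA-poor arm, so model-based estimates from that point on could change.

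**Working it through.** **The plan's own figure.** Section 8.1.1 gives 19 enrolled as 12 and 7, with 10 and 6 completers. Rounding down: 19 x 2/3 gives 12, leaving 7; 12 x 0.85 = 10.2 gives 10; 7 x 0.90 = 6.3 gives 6. This reproduces, with 2:1 applied to everyone.

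**Inputs.** The 8.1.2 frequencies for 2/2, 2/3, 3/3, 2/4, 3/4 and 4/4 are 1, 10, 62, 2, 20 and 5%. So ApoE3 = 62 + 2 = 64% and variants = 1 + 10 + 20 + 5 = 36% (E2 11%, E4 25%).

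**Built-in gap.**
- Share on oil = 0.64 x 2/3 + 0.36 x 1/2 = 0.607, or about 11.5 v 7.5 of 19.
- Variant share on oil = 0.18/0.607 = 29.7%.
- Variant share on usual care = 0.18/0.393 = 45.8%.
- Gap = 16.1 points. If variants are 20% to 45% of enrollees (an assumed range), it is 11.5 to 17.1 points.

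**Weight on variants in the treatment contrast.** Unadjusted, 0.297. With an additive stratum term, 0.36 x 0.25 / (0.36 x 0.25 + 0.64 x 2/9) = 0.388. In the population, 0.36. If apoE modifies the oil effect by D, the shift is (0.297 - 0.36)D = -0.063D without the term and +0.028D with it.

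**Consequences by pattern.** D, the apoE difference in SD units, is not in the documents; D = 1 is assumed, with residual variance 1. Interval ratios are from simulation (12,000 runs per setting) with assumed blocks of 2 in variants and of 3 in two ApoE3 triglyceride strata, 20% of subjects at or above 350 mg/dL, and the plan's 15% and 10% dropout.

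| Pattern | Shift without / with term | Residual variance without / with | Interval width, with ÷ without (N = 19 / 40) |
|---|---|---|---|
| No apoE effect (D = 0) | 0 / 0 | 1.00 / 1.00 | 1.027 / 1.018 |
| All variants differ, both arms | -0.161 / 0 | 1.224 / 1.000 | 0.924 / 0.916 |
| Only E2 differs, both arms | -0.049 / 0 | 1.097 / 1.076 | 1.016 / 1.007 |
| Oil effect modified, all variants | -0.063 / +0.028 | 1.127 / 1.055 | 0.994 / 0.986 |
| Oil effect modified, E2 only | -0.019 / +0.008 | 1.050 / 1.043 | 1.023 / 1.013 |

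**Bias against noise.** If all variants differ in both arms, simulated bias over standard error is 0.156/0.518 = 0.30 at N = 19 and 0.161/0.350 = 0.46 at N = 40. If only E2 differs, it is 0.047/0.532 = 0.09 and 0.047/0.365 = 0.13.

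**Chance imbalance.** Under the same blocks, 95% of simulated trials have a completer gap between -7 and +39 points at N = 19, and between +2 and +30 at N = 40.

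**Type I error without the term** (all variants, both arms, D = 1). With stratified blocks it is 4.4% at 19 enrolled and 5.0% at 40. With simple randomisation within apoE group it is 5.2% at 16 analysed and 7.0% at 34. With the term it is about 5% in the simple-randomisation runs.

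**Form of the term.** In one simulated two-period data set of 60 subjects, the period x treatment estimate was 0.5285 both without apoE and with an apoE main effect. It moved to 0.558 only when apoE x period was added.

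**The case against.** The best counter-argument is that no documented route leads from the gap to bias. Section 8.1.2 speaks of effect modification, not of apoE-related change without treatment, and 5.4.1 says "we do not expect the results to be influenced by a secular trend". If oil works in no stratum, effect modification produces neither bias nor false positives. If it does work, the additive term only exchanges a shift of -0.063D for +0.028D.

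The larger figures also need E2 and E4 to move together. The fish-oil row of the table in 8.1.2 does not show that: for triglycerides E4 matches E3 and only E2 differs, and for HDL the two variants go in opposite directions. The triglyceride entries point to the last row of the table above, with a shift of 0.019D, about 0.04 standard errors at N = 19 (0.019/0.52), and a slightly wider interval after the change. In addition, 8.3 is a general approach pending a SAP, the pilot's aim is estimation, and parsimony is reasonable with 16 expected completers.

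Most of this stands, and it limits the size of the point. It does not remove it. Section 8.3 already classes apoE as exploratory, and nothing says the SAP will change that. The interim revisit in 8.1.2 is about a possible crossover substudy, not the model. The fish-oil row does not report VLDL-apoB production, the primary endpoint. And 0.388 is nearer to 0.36 than 0.297 is.

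**Conclusion.** The concern holds, as a minor point. The 16.1-point expected imbalance follows directly from the plan's ratios and genotype frequencies, and the factor that creates it has no fixed place in the main model. Any harm is conditional: bias of 0.16 x D requires all variants to change differently in both arms, and neither that pattern nor D is given in the documents. At pilot size the bias is small beside the standard error, and type I error is not materially inflated at 19 enrolled (4.4% to 5.2% in the worst pattern at D = 1, depending on the assumed randomisation scheme). A gain in precision cannot be relied on. The case for the term is that the analysis should match the randomisation, that the imbalance does not fade if the sample is enlarged, and that the cost is low.

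**What to change.** In 8.3 or the SAP, pre-specify the apoE allocation stratum in the main model, using the 8.1.2 grouping: ApoE3 (3/3, 2/4) v ApoE2/E4 (2/2, 2/3, 3/4, 4/4). Enter it as apoE stratum x period in the mixed model, or as a covariate in an ANCOVA of the on-treatment value. An apoE main effect alone does not adjust period x treatment. Report the residual SD with and without the term, since the pilot's SD will feed later design. Keep separate E2 and E4 terms, and apoE x treatment, exploratory.

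The cost is wording only; randomisation and data collection do not change. The model loses one error degree of freedom: for a two-group comparison of change in 16 completers, 14 falls to 13 and the t critical value rises from 2.145 to 2.160. If apoE is irrelevant, the interval is about 3% wider at 19 enrolled and 2% wider at 40.
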